Brand appeal: Participants will be asked to complete a 6-item measure of brand appeal regarding their preferred brand and the two study-supplied cigarettes they smoked during their in-person session. They will be asked to rate the design of the brand of cigarette they currently smoke (or just tried) on the following 6 items: 1) stylish, 2) fashionable, 3) cool, 4) high quality, 5) attractive, and 6) appealing. Responses will be scored using a 7-point likert scale with anchors of “Strongly Agree” and “Strongly Disagree.”

Mouth-level nicotine exposure and compensatory smoking: We will collect and store the filters of the two cigarettes smoked during laboratory sessions for potential future analysis regarding mouth-level nicotine exposure (approximated using the biomarker, solanesol) and compensatory smoking (estimated via digital image analysis).

2. Group Modifications:

There will be no differences in study procedures or questionnaire administration; all participants will complete the same procedures and questionnaires following randomization to filter type and packaging conditions.

3. Method for Assigning Subjects to Groups:

Participants will be randomly assigned to smoke two study-supplied cigarettes from 4 possible combinations of filter type and packaging conditions:

1. Charcoal filter cigarette in light-colored pack (NAS Sky cigarette in NAS Sky pack [i.e., actual product])
2. Charcoal filter cigarette in black-colored pack (NAS Sky cigarette in NAS Black pack)
3. Non-charcoal filter cigarette in light-colored pack (NAS Orange cigarette in NAS Sky pack)
4. Non-charcoal filter cigarette in black-colored pack (NAS Orange cigarette in NAS Black pack)

Each participant will smoke one charcoal filtered and one non-charcoal filtered cigarette, in counterbalanced order (i.e., the within-subject condition), but the participant will be assigned the same package color for both cigarettes (i.e., the between subject condition). Randomization group (filter order and package color) will be determined via internal database and assigned prior to participants' arrival for the session.

4. Administration of Surveys and/or Process:

The following measures will be assessed by staff at the start of the laboratory session:

1. Session onset CO
2. Medical history
3. Height and weight
4. Cigarette brand characteristics

The following measures will be completed by participants prior to trying to smoking any laboratory cigarettes:

1. Demographics
2. EtOH

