Data Processing: The data entry screens will resemble the data collection forms as closely as possible to allow visual referencing during data entry. This data entry module will be configured for single data entry. Participant data will either be entered into REDCap using smart phones, computers, or tablets or be collected by research staff, recorded on study-specific CRFs, and scanned in or entered directly into the appropriate DMS module. Data entry checks will be included in the entry screen designs where appropriate to limit the opportunity for erroneous entries due to mistyping. Such data entry checks would include value range comparisons, valid data type checks, required value checks, and/or skip pattern enforcement. Following telephone eligibility screening, staff will perform subject registration. A randomization module will allow staff to randomize eligible subjects into one of the four randomization groups. At the randomization attempt, the DMS will check the eligibility data to confirm validity. A randomization assignment will then be provided.

Data Quality Assurance: The Data Manager will work closely with the PI to develop a data quality module that will identify data items that may have been collected or entered into the database incorrectly. The module will run automatically to inspect all newly entered or modified data. Staff will review data validation results and take any required corrective action for invalid data. Queries will be recorded and tracked in the data quality module.

Corrections identified for individual data items will be managed by the research staff. All changes made will be recorded in an electronic audit trail and documented using change control procedures.

Monitoring of study progress will be accomplished, in part, through reviewing a set of standard enrollment, tracking, and quality review monitoring reports created by the Data Manager. Data audits will occur after the first participants are enrolled, as well as periodically throughout the recruitment period, to detect data entry errors. Eligible participants will have their source document information compared with the data entered in the database. Any errors will be investigated, resolved, and a plan will be implemented to prevent further errors should concerning patterns emerge.

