Individuals will not benefit directly from their participation in this study. The anticipated benefit of this research to society (i.e., indirect benefit) is to provide data regarding the effects of cigarette filter composition and packaging on product perception, use, and exposure outcomes, which may be used to guide decisions related to regulating cigarette design and marketing.

Although this study is not a cessation trial, participants may be motivated to seek cessation. Information about ongoing cessation trials in our Center and in the City of Philadelphia is available for participants interested in cessation.

3. Subject Privacy:

Only individuals who have responded to recruitment efforts or who have agreed to be contacted about studies at our Center will be contacted over the phone. If an individual cannot be reached immediately, staff will identify themselves only as calling from the University of Pennsylvania; no mention will be made of the inquiry regarding study participation. Participants will undergo an initial telephone screening where preliminary eligibility for the study will be determined. Only if a participant is initially eligible will they be asked to attend an in-person visit to confirm eligibility. All data will be collected by staff who have completed the CITI-Protection of Human Subjects Research Training and HIPAA Compliance Training. Once enrolled, information will never be recorded with identifiers other than study ID. A separate list of names with ID numbers will be accessible only by authorized personnel. All records will be kept in locked filing cabinets to maintain confidentiality. All analyses will be conducted on de-identified data.

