- Authorized members of UPENN Staff (e.g. accounting and billing matters, provide treatment, etc.)
- UPENN IRB
- Greenphire
- Office of Clinical Research
- The Office of Human Research Protections
- The Food and Drug Administration (FDA)
- The National Institutes of Health

6. Compensation:

Participants will be compensated up to \$100 via ClinCard for successfully completing all study requirements at the end of the single laboratory session (\$90 visit compensation, \$10 travel reimbursement). Those determined to be ineligible during the study session will receive travel compensation only (\$10).

Participants will be asked to complete a W-9 tax form at the conclusion of the study because the University of Pennsylvania is required to report to the Internal Revenue Service (IRS) any cumulative payments for participation in research studies at the University of Pennsylvania that exceed a total of \$600 in a calendar year. A W-9 will aid the Center in tracking and reporting those who participate in multiple projects at the Center and accrue over \$600 in a calendar year.

7. Data and Safety Monitoring:

The PI will be responsible for the overall monitoring of the data and safety of participants, assisted by other study personnel. Any unanticipated problems, serious and unexpected adverse events, deviations or protocol changes will be promptly reported by the PI or designated member of the research team to the IRB.

8. Investigator's Risk/Benefit Assessment:

The PI feels the benefits of study participation outweigh the risks, given that the risks of participating in this study are minimal and largely relate to confidentiality/privacy concerns, and that the anticipated benefits to society include increased knowledge of how cigarette packaging and filtration influence product perceptions, use, and exposure, which by extension, may be used to inform regulation of both cigarette marketing and design to subsequently reduce tobacco-caused disease.

INFORMED CONSENT:

1. Consent Process:

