A fully trained study staff member will obtain informed consent using the combined consent and HIPAA authorization form approved by the University of Pennsylvania IRB. The consenting process will occur in-person at the CIRNA prior to the initiation of any study procedures and will involve a discussion of the study requirements and procedures. Participants will have an opportunity to ask any questions and/or express concerns, which will be documented on a "Questions Form." Participants can elect not to participate and may withdraw at any time without penalty. Participants will receive a copy of the combined consent and HIPAA authorization form for their records. In addition, participants will be given the Principal Investigator's contact information (located on the consent) should they wish to speak to the Investigator during the course of the study regarding their consent or the study procedures. The consent process will take place in English. There will be no waiting period, no coercion

to participate, and all participants will be considered competent to provide informed consent (i.e., they will be asked if they understand what they are consenting for). If the participant has difficulty or is unable to understand the consent form or other procedures, they will be excluded from the study. The original signed combined consent/HIPAA authorization and Questions forms will be centrally stored in Regulatory Consent Binders.

2. Waiver of Informed Consent:

Not applicable.

RESOURCES NECESSARY FOR HUMAN RESEARCH PROTECTION:

1. Qualifications of Investigators

Brief highlights are presented below for key investigators.

[name]., Principal Investigator: [name] is an Assistant Professor in the Center for Interdisciplinary Research on Nicotine Addiction (CIRNA) in the Department of Psychiatry and the Tobacco Center of Regulatory Science at the University of Pennsylvania (UPENN). She will oversee operations for the study and will have responsibility for the design, implementation, and evaluation of the proposed research. [name] has previously conducted laboratory-based smoking studies of similar design and duration related to informing the tobacco regulatory science field. She will be responsible for overseeing the study materials for institutional review board approval, programming study equipment, overseeing training, conducting analyses and manuscript preparation.

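### Pack colour and filter order are assigned before arrival, ahead of consent and in-person eligibility checks; releasing the assignment later is a cheap, low-impact improvement

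*Combined protocol and SAP*

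**What the plan says.** **Assignment.** Methods, 3. Method for Assigning Subjects to Groups fixes the timing of the group: "filter order and package color) will be determined via internal database and assigned prior to participants' arrival for the session". Pack colour is the same for both of a participant's cigarettes, so it is the between-subject factor.

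**Database steps.** Methods, 5. Data Management (Data Processing) gives the sequence. It starts from the telephone screen: "Following telephone eligibility screening, staff will perform subject registration". Allocation comes next and is run by staff: "A randomization module will allow staff to randomize eligible subjects into one of the four randomization groups". One safeguard applies at that moment: "At the randomization attempt, the DMS will check the eligibility data to confirm validity". The last step is release of the group: "A randomization assignment will then be provided".

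**Consent.** Informed Consent, 1. Consent Process: "The consenting process will occur in-person at the CIRNA prior to the initiation of any study procedures".

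**Eligibility.** Risk/Benefit Assessment, 3. Subject Privacy: "Only if a participant is initially eligible will they be asked to attend an in-person visit to confirm eligibility". Study Procedures, 1. Detailed Description puts the own-pack check first at the visit, then consent, the CO reading, the medical history, the questionnaires and the first cigarette.

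**In-session exclusion is foreseen.** Risk/Benefit Assessment, 6. Compensation: "Those determined to be ineligible during the study session will receive travel compensation only". Target Population and Accrual plans 60 consented for 40 completers and expects some to prove ineligible or to withdraw, without splitting the two.

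**Analysis.** Study Procedures, 5. Statistical Analysis first fits main and interaction effects alone, then adds any baseline variable associated with the outcome at p < 0.25.

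**The concern.** Because the group is fixed before arrival, the system's eligibility check at randomization can use only pre-visit data. It cannot cover the CO reading, sight of the participant's own pack, or the in-person medical history.

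Some of what follows needs judgement. Serious disease and impairments are assessed case by case, a forgotten pack may lead to rescheduling or exclusion at the PI's discretion, and the general exclusion reasons can be applied at any point (Key Exclusion Criteria; Detailed Description). If the person deciding knows the pack colour, exclusions could differ by pack arm, and the two arms would no longer be comparable by randomization alone.

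The exposed comparison is the between-subject pack contrast (Aim 2). The filter contrast is within-person. The interaction (Aim 3) compares within-person differences, so it is affected only if the trait behind the exclusions also predicts a person's filter difference.

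**Working it through.** **1. Order of events.** Telephone screen, then registration and assignment, then arrival, own-pack check, consent, CO, medical history, questionnaires, first cigarette. Data Processing taken alone could be read as allowing randomization at the visit; the assignment section rules that out. Up to 60 − 40 = 20 of 60 consented (33%) may be lost, all after assignment. Losses at the own-pack check, and people who never attend, come before consent and would be additional.

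**2. The plan's own figure.** Inputs from Statistical Analysis: partial η² = .05, α = .05, within-subject correlation ρ = .5, N = 40, two measurements per person.
- f² = .05/.95 = .0526
- λ = f² × N × m/(1 − ρ) = .0526 × 40 × 2/.5 = 8.42, on F(1, 38)
- Interaction power = .807, which reproduces the stated 80%.

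**3. Random loss.** Assume equal pack arms at assignment and 40 completers left at random. λ is scaled by n₁n₂/400 and power averaged over the hypergeometric distribution of the pack split.

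| Assigned | Power |
|---|---|
| 44 | .806 |
| 60 | .804 |
| 70 | .803 |
| 80 | .802 |

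The largest cost is .807 − .802 = .005. Totals above 60 allow for people assigned but never consented, which is an assumption.

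**4. Arm-aware loss, unadjusted pack contrast.** These inputs are assumptions, not document figures: 30 assigned and 10 lost per pack arm; no true effect; outcome SD 1. In one arm, k of the 10 losses are the k people highest on a baseline trait that correlates r with the person-mean outcome. All other losses are random.
- SD of a person's mean over two cigarettes = √((1 + .5)/2) = .866
- SE of the pack contrast = .866 × √(2/20) = .274
- Expected shift = r × .866 × (sum of the k largest expected normal order statistics of 30)/(30 − k)
- k = 1: 2.043/29 = .070, so the shift is .018 (r = .3) or .031 (r = .5)
- k = 5: (2.043 + 1.616 + 1.365 + 1.179 + 1.026)/25 = .289, so the shift is .075 or .125

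Simulation (120,000 runs per case) agrees:

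| r | k | Shift (SD) | Type I error |
|---|---|---|---|
| .3 | 1 | .018 | 5.1% |
| .3 | 3 | .048 | 5.3% |
| .3 | 5 | .075 | 5.9% |
| .5 | 1 | .032 | 5.2% |
| .5 | 3 | .082 | 6.3% |
| .5 | 5 | .126 | 7.6% |

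**5. With the planned covariate step.** If the trait is a recorded baseline variable and enters whenever p < .25 (73% to 98% of runs), the shift is at most .006 SD and type I error 4.9% to 5.0%. If the trait is not recorded, such as a staff impression, the figures in step 4 stand.

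**6. Interaction.** In the same runs the shift is at most .001, with type I error 4.9% to 5.1%. If the trait also correlates .3 to .5 with the filter difference (SD = √(2 × (1 − .5)) = 1; SE = √(2/20) = .316), the shift is .020 to .037 at k = 1 (5.1% to 5.3%) and .088 to .146 at k = 5 (6.0% to 7.8%).

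**The case against.** The strongest reply is that this hardly matters. Harm needs a person who knows the arm, discretion used unequally by pack, a trait linked to the outcome, and a trait that was not recorded. The documents show none of these. That stands, and it is why the point is graded low.

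The upper case is also generous. Participants arrive one at a time, with capacity for two a day, so nobody could rank 30 people and remove the top five. The CO limit is a fixed rule, someone who withdraws before the first cigarette is not described as having seen the study pack, and the protocol expects no significant retention problem. One selective loss is more realistic than five.

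Concealment may also exist in practice. Data Storage limits database functions by role, changes are audit-trailed, and study SOPs are mentioned. The SOPs and a short part of the Resources section were not available. Concealment is therefore undocumented here, not shown to be absent.

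Three stronger readings are tempting, and the text does not support them:
- A reader might infer that exclusions were or will be steered by pack. Nothing says so.
- A reader might infer a breach of the consent rule. The protocol does not say whether assignment counts as a study procedure.
- A reader might infer that upcoming packs can be predicted from the block structure. No blocks are specified, so no block-size advice follows.

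**Conclusion.** The point holds as a cheap improvement with low impact. The order of events is plain: assignment precedes consent and every in-person check, some of those checks are discretionary, and the available text does not conceal the arm from those deciding.

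The consequence is hypothetical and small: about .02 to .03 SD on the unadjusted pack contrast for one selective loss, and .08 to .13 SD in an extreme case, against an SE of .27. These sizes rest on the assumed loss pattern and correlations in step 4. Adjustment deals with recorded traits; bias from an unrecorded one could be neither ruled out nor corrected afterwards. The sample size and its stated power are unaffected.

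**What to change.** Amend the assignment section and Data Processing so that the randomization module releases the assignment at the visit only once consent, in-person eligibility and the baseline questionnaires are recorded as complete, immediately before the first cigarette. Keep the upcoming assignment hidden from session staff until then. Report any exclusion or withdrawal after release by arm, with reasons.

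The module already has an eligibility gate, so this is a short amendment and a change of timing. It also means that own-brand baseline ratings are finished before anyone in the session can know the arm. The cost is practical: both pack types and both filter orders must be ready at each visit. No extra participants are needed.

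The change does not close everything. Discretionary exclusion and discontinuation remain possible once the pack is in view (Key Exclusion Criteria; Early Withdrawal of Subjects), which is why the report by arm is part of the fix. If release at the visit is impractical, masking whoever judges eligibility to the assignment would serve the same purpose.

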4. FTCD
5. Contemplation ladder
6. Craving (QSU)
7. Withdrawal (WSCW)
8. Risk beliefs (own brand)
9. Perceived health risks (own brand)
10. Purchase task (own brand)
11. Brand appeal (own brand)
12. Pre-cigarette CO reading(s)

The following measures will be completed by participants after each cigarette smoked during the session:

1. Post-cigarette CO reading(s)
2. Subjective ratings
3. Risk perceptions
4. Perceived health risks
5. Attitudes and intentions
6. Purchase task
7. Brand appeal

The following measures will be completed by participants at the conclusion of the session:

1. Final cigarette rating scale
2. NAS & charcoal knowledge

5. Data Management:

A data management system (DMS) developed by the CIRNA Data Management Team will facilitate the operational facets of this study, including determining initial eligibility and producing lists of subjects for telephone contacts for scheduling, and data entry. The DMS uses the relational database product Microsoft Access as the primary software platform for data entry and validation, storage, retrieval, modification, and security. The DMS ensures data integrity through range and validity checks during the data entry process. Daily backups are performed to protect data from accidental destruction or corruption.

The CIRNA Data Manager will work closely with the PI, [name], to develop an understanding of the data collection, storage, and quality assessment needs for the study (e.g., design and development of data collection forms and any additional administrative CRFs) to ensure that standardized, uniform data collection and management procedures throughout the duration of study enrollment. The Data Manager will work closely with the PI and senior personnel to design, develop, and test an appropriate database structure to support the requirements of the DMS and to promote data security and integrity. Electronic audit trails of changes to database contents are incorporated into the design and will capture and record those changes automatically. In addition to the study database where actual results will be maintained, a development database will be created. The development database is a working environment that facilitates the development, testing, troubleshooting, enhancement, and training for the DMS without adversely affecting the integrity of the collected project data.

Prior to deployment for use by study staff, the database and DMS will be subjected to extensive functional testing according to a written test plan intended to verify the proper functioning of all DMS components. Any components that do not function as intended will be identified and evaluated by the development team to determine appropriate corrective action. Testing will also include an evaluation by user representatives for adherence to the requirements established by the intended users for the DMS. Successful completion of user acceptance tests will mark the end of development and predicate the deployment of the DMS for use in storing and managing active trial data. Any modifications made to the DMS will be conducted in accordance with change control procedures.

Data Storage: All data will be stored in an electronic Access database or in REDCap, and will be managed by the Data Manager. The database will be hosted on a secure computing server and will be restricted to individuals authorized to work on the trial via individual user accounts with passwords. Specific privilege assignments within the database will also be employed to limit the types of functions that authorized users can perform to those that are appropriate for their role in the trial. Additional measures to prevent unauthorized external access to the database will be employed using network firewall technologies. The Data Manager will maintain the database in an appropriate manner for the retention period required by regulation. Database administration includes user account maintenance, database security, performance monitoring, and database change management.

Data Processing: The data entry screens will resemble the data collection forms as closely as possible to allow visual referencing during data entry. This data entry module will be configured for single data entry. Participant data will either be entered into REDCap using smart phones, computers, or tablets or be collected by research staff, recorded on study-specific CRFs, and scanned in or entered directly into the appropriate DMS module. Data entry checks will be included in the entry screen designs where appropriate to limit the opportunity for erroneous entries due to mistyping. Such data entry checks would include value range comparisons, valid data type checks, required value checks, and/or skip pattern enforcement. Following telephone eligibility screening, staff will perform subject registration. A randomization module will allow staff to randomize eligible subjects into one of the four randomization groups. At the randomization attempt, the DMS will check the eligibility data to confirm validity. A randomization assignment will then be provided.

Data Quality Assurance: The Data Manager will work closely with the PI to develop a data quality module that will identify data items that may have been collected or entered into the database incorrectly. The module will run automatically to inspect all newly entered or modified data. Staff will review data validation results and take any required corrective action for invalid data. Queries will be recorded and tracked in the data quality module.

Corrections identified for individual data items will be managed by the research staff. All changes made will be recorded in an electronic audit trail and documented using change control procedures.

Monitoring of study progress will be accomplished, in part, through reviewing a set of standard enrollment, tracking, and quality review monitoring reports created by the Data Manager. Data audits will occur after the first participants are enrolled, as well as periodically throughout the recruitment period, to detect data entry errors. Eligible participants will have their source document information compared with the data entered in the database. Any errors will be investigated, resolved, and a plan will be implemented to prevent further errors should concerning patterns emerge.

The Data Manager will develop a module to assist study staff in participant recruitment and retention tracking. This module will accept and store contact information for potential subjects and will include data items to indicate the completion status of significant events. The tracking module will include information about contact and visit schedules to assist in preparing communications to potential and active participants concerning scheduled events. The module will also allow for incentive-related inventory management.

6. Subject Follow-up:

Not applicable. We will not follow up with participants after they complete the single study visit.

STUDY PROCEDURES:

1. Detailed Description:

Telephone eligibility interview (duration: ~0.5 hours): Trained personnel will determine participants' initial eligibility during a structured telephone interview. Those who meet eligibility criteria will be scheduled for the in-person visit.

Laboratory visit (duration: ~2.5 hours): The single study visit will occur at the Center for Interdisciplinary Research on Nicotine Addiction (CIRNA). Upon entering the CIRNA for this session, participants will complete the following:

1. Confirm the accuracy of information (i.e. name, address, phone number, email [if applicable], date of birth, age, ethnicity, race, and cigarette brand type) provided during the initial Telephone Eligibility Screening.
 - a. Participants must bring in a pack of their own preferred brand of cigarettes to verify their cigarette brand type.
 - i. If a participant forgets to bring a pack of their preferred brand of cigarettes, their session may be rescheduled to a later date or the participant may be deemed ineligible at the discretion of the PI.
2. Hear a study description where all study procedures will be reviewed.
 - a. The combined informed consent and HIPAA will be read verbatim. All questions will be answered as appropriate after which the combined informed consent and HIPAA form will be completed (signed and dated) by the participant and a member of the research staff.
3. Perform a CO breath assessment and self-report smoking behavior over the past 24 hours to control for prior tobacco exposure.
 - a. Participants with a CO reading < 5 ppm will be ineligible.
4. Height and weight measurements.
5. Complete a Medical History Form with a member of the research staff to review for applicable contraindications previously listed under Key Inclusion/Exclusion Criteria.
6. Complete questionnaires on cigarette characteristics (Cigarette Brand Form_*Staff should physically view preferred brand of cigarette pack), demographics, ETOH history, smoking history, nicotine dependence (FTND), craving (QSU), withdrawal (WSC), quitting motivation (contemplation ladder), risk perceptions (Risk Beliefs & Perceived Health Risks), Purchase Task, and Brand Appeal.

7. Smoke two study provided cigarettes interspersed by 45 minutes in the smoking lab while video-recorded.
 - a. Participants will complete a harm perceptions questionnaire before smoking each cigarette.
 - b. CO will be assessed before and after each cigarette smoked in the lab.
 - c. Subjective Cigarette Ratings (VAS), Risk Beliefs, Perceived Health Risks, Purchase Task, Attitudes/Intentions, and Brand Appeal will be assessed after each cigarette smoked in the lab.
 - d. Used cigarette filters will be collected and stored for potential future analysis.
8. Complete the Final Cigarette Rating Scale and NAS & Charcoal Knowledge questionnaires.
9. Receive Debrief Script and study payment
 - a. Participants will be debriefed as to the full purpose of the study and compensated for their time.

2. Data Collection:

As detailed in the Data Management section, we will use both paper and electronic forms (via REDCap) surveys to collect participant data.

3. Genetic Testing:

Not applicable.

4. Use of Deception:

To avoid biasing participants' perceptions and use of the study cigarettes, we will not explicitly state in any materials (e.g., flyers, consent form) that the study's purpose is to evaluate the effects of cigarette packaging and filter composition. Instead, individuals will be told that we are recruiting volunteers to "evaluate different commercially available cigarettes."

Deception is acceptable in the present study because the study is minimal risk, and participants will be debriefed within the same session that the deception occurs.

Deception is necessary and scientifically valid in this instance because we are interested in how certain design and marketing features used to promote cigarettes implicitly affect smokers' perceptions and use of those products; if we were to inform participants that we were specifically interested in their reactions to the filter and packaging, they may respond in ways that they otherwise would not.

To inform subjects prospectively of the use of deception/incomplete disclosure, we have included the following suggested consent language on our consent document (see Informed Consent document): "In some research studies, the investigators cannot tell you exactly what the study is about before you participate in the study. We will describe the tasks in the study in a general way, but we can't explain the real purpose of the study until after you complete these tasks. When you are done, we will explain why we are doing this study, what we are looking at, and any other information you should know about this study. You will also be able to ask any questions you might have about the study's purpose and the tasks you did. Though we may not be able to explain the real purposes of the study until after you complete the tasks, there are no additional risks to those that have been described in this consent form."

Upon completing the full survey, participants will be debriefed of the true study purpose. They will be told that we were specifically interested in understanding the effects of cigarette packaging and filter type on their perceptions and use of the product, and that we were initially vague about our procedures to avoiding biasing their responses toward the study manipulations.

5. Statistical Analysis:

Analytic plan. Main and interaction effects of filter and pack type will be analyzed using univariate analysis of variance (ANOVA) models in SPSS IBM Statistics v26. Primary outcomes are continuous, and based on previous work^{17,21,22} are expected to meet normality assumptions. Analyses will first include only main and interaction effects, then will include as covariates any baseline variables demonstrating a bivariate association of $p < 0.25$ with a given outcome measure.

Power analysis and sample size. A priori power analyses were conducted for primary aims using G*Power v3.1.9.2. These analyses determined that a target sample size of 40 will be adequate to detect a significant small-to-medium effect (partial $\eta^2 = .05$, $\alpha = 0.05$, within-subject correlation = 0.5) of the 2 x 2 between-within subject interaction on a univariate outcome with 80% power.

RISK/BENEFIT ASSESSMENT:

1. Risks:

The potential risks to participants, and their likelihood and seriousness, are minimal and described below. Participants can choose, as an alternative, to not enroll in this study.

Emotional distress: Some subjects may experience some emotional distress during the study due to learning their CO levels or completing questionnaires. These events happen very rarely and in almost all cases are short-lived and of low intensity. If upon assessment in the study the participant exhibits severe high levels of emotional distress, the participant will be offered a referral for mental health services in the area.

Cigarette smoking: Although smoking is associated with many diseases, we do not believe the risk is beyond everyday risk as all participants must report smoking at least 5 cigarettes per day to be eligible for this study, which exceeds the number of cigarettes that they would smoke during the single study session. We will inform participants that continued smoking has been shown to cause diseases such as emphysema and cancer.

Confidentiality and loss of privacy: Communications made among study staff regarding participants will use study identification number only and not include names or any other personal identification numbers. Participant data will be kept in locked files which are only accessible to staff. In all data sets we will only include identification numbers to label each participant. No names or other unique identifiers will appear in data sets. Only study-specific staff, identified in institutional review board-approved materials, will have access to the list of names matched to identification numbers.

COVID-19: By attending the laboratory visit, participants may place themselves at increased risk for exposure to the COVID-19 virus. Additionally, if participants choose to use public transportation to get to their appointments, they may place themselves at increased risk for exposure to the COVID-19 virus. We advise participants to wear a mask and practice social distancing while using public transportation. All participants will be provided the IRB recommended COVID-19 Informational Sheet before agreeing to take part in this research study. The CIRNA will follow guidelines to ensure minimal contact between participants and staff to mitigate exposure to the COVID-19 virus. Details can be found within the Spring Semester Research Resumption Phase Plan for the 4th Floor.

Other risks: This research may involve risks that are currently unforeseeable.

2. Benefits:

Individuals will not benefit directly from their participation in this study. The anticipated benefit of this research to society (i.e., indirect benefit) is to provide data regarding the effects of cigarette filter composition and packaging on product perception, use, and exposure outcomes, which may be used to guide decisions related to regulating cigarette design and marketing.

Although this study is not a cessation trial, participants may be motivated to seek cessation. Information about ongoing cessation trials in our Center and in the City of Philadelphia is available for participants interested in cessation.

3. Subject Privacy:

Only individuals who have responded to recruitment efforts or who have agreed to be contacted about studies at our Center will be contacted over the phone. If an individual cannot be reached immediately, staff will identify themselves only as calling from the University of Pennsylvania; no mention will be made of the inquiry regarding study participation. Participants will undergo an initial telephone screening where preliminary eligibility for the study will be determined. Only if a participant is initially eligible will they be asked to attend an in-person visit to confirm eligibility. All data will be collected by staff who have completed the CITI-Protection of Human Subjects Research Training and HIPAA Compliance Training. Once enrolled, information will never be recorded with identifiers other than study ID. A separate list of names with ID numbers will be accessible only by authorized personnel. All records will be kept in locked filing cabinets to maintain confidentiality. All analyses will be conducted on de-identified data.

